## 1. INTRODUCTION

### 1.1 BACKGROUND

#### 1.1.1 HUMAN PAPILLOMAVIRUS AND INFECTION

Human papillomaviruses (HPV) are double-stranded DNA viruses with more than 100 genotypes some of which can lead to malignant neoplasia, localized primarily in the anogenital area and aerodigestive tract, in both men and women. HPV types tropic to mucosal tissues are classified into high-risk (HR), based on their potential to cause cancer, and low-risk (LR) causing generally benign lesions. HPV-16 and HPV-18 are the most significant amongst high-risk types since they are responsible for most HPV-caused cancers [1].

HPV-16 is involved in more than 85% of HPV-associated vulvar HSIL cases in the U.S.[1]. Persistent infection with one or more oncogenic (high-risk) HPV genotypes can lead to the development of precancerous, histologic high grade squamous intraepithelial lesions (HSIL).

HPV causes more cancers than any other virus. In U.S. archival tissues of cancers diagnosed from 1993 to 2005, HPV DNA was detected in 68.8% of vulvar, 90.6% of cervical, 91.1% of anal, 75.0% of vaginal, 70.1% of oro-pharyngeal, 63.3% of penile, 32.0% of oral cavity, and 20.9% of laryngeal cancers, as well as in 98.8% of cervical cancer in situ (CCIS)[2].

#### 1.1.2 VULVAR CANCER

Vulvar HSIL can lead to vulvar cancer with an estimated 5,950 new cases and 1,110 attributable deaths annually for year 2016 in the United States [3]. Vulvar cancers consist largely of squamous cell carcinomas and accounts for approximately 5% of all female genital malignancies [4]. Differentiated VIN, which is typically not caused by HPV infection and is more typically found in older women, is more likely to progress to cancer more rapidly than HPV-associated-VIN. The five year overall relative survival for vulvar cancer in the U.S. is 70.7% [3]. Recurrent vulvar cancer occurs in an average of 24% of cases after primary treatment, after surgery with or without radiation [5].

#### 1.1.3 VULVAR INTRAEPITHELIAL NEOPLASIA (VULVAR HSIL)

HPV-associated vulvar intraepithelial neoplasia (VIN) is a chronic (typically persisting for years), premalignant disorder of the vulvar skin that is caused by persistent infection with one or more high-risk genotypes of HPV. Infected cells produce E6 and E7 oncoproteins constitutively, which increases the degradation of cell cycle regulation proteins p53 and pRb, respectively, resulting in unrestricted cell growth and neoplasia. The basis for progression to cancer is, therefore, attributed to the viral proteins E6 and E7. VGX-3100 specifically induces immune responses against E6 and E7, thereby enabling clearance of pre-malignant cells as demonstrated in the Phase 2 study of cervical HSIL [6]

In 2004, the International Society for the Study of Vulvovaginal Disease (ISSVD) replaced the three grade classification system with the current single grade classification for which

only high grade VIN (2/3) is classified as VIN [7]. In 2012, the Lower Anogenital Squamous Terminology (LAST) Standardization Project for HPV-associated lesions applied the term high grade squamous intraepithelial lesion (HSIL) to encompass high grade dysplasia [8]. Therefore, for the purpose of this study, the term vulvar HSIL will be used, which encompasses VIN 2 and VIN 3; the term 'vulvar LSIL' will be used to encompass what was previously known as VIN 1.

Once vulvar HSIL has developed, spontaneous regression is rare, likely occurring in only 1.5% to 5% of women [9]. Over time, typically years, vulvar HSIL can progress to invasive cancer of the vulva, e.g. from treated patients, median: 2.4 years in one group and median 13.8 years in another group [10], and from VIN3 patients, mean = 2.5 years, range: 4 – 216 months [11].

Vulvar HSIL remains a significantly undermet medical condition for the following reasons which will be described further: 1) the rate of recurrence of vulvar HSIL under currently used surgical and medical approaches is extremely high, 2) there is a high psychological and physical negative impact of surgery, 3) vulvar HSIL is symptomatic and impacts activities of daily living, 4) prophylactic HPV vaccines have no therapeutic activity against vulvar HSIL and have not achieved universal uptake, leaving a population of susceptible and impacted women, and 5) the early diagnosis of vulvar HSIL is limited to visual inspection with biopsy.

#### 1.1.4 RECURRENT DISEASE WITH CURRENT THERAPEUTIC OPTIONS

There remains an unmet medical need with regard to effective treatment options for vulvar HSIL. Current treatment options show a significant risk of vulvar HSIL recurrence, often requiring multiple, repeat treatments. Progression to vulvar cancer following current vulvar HSIL treatments can also occur within 1 year of treatment and for up to 20 years post treatment. The current treatment options for vulvar HSIL are surgical excision, laser ablation, and off-label medical therapy. The rate of HPV-associated vulvar HSIL recurrence after surgical treatment is high; post-treatment recurrence rates exceed 30-50% with all currently available treatment regimens [12, 13].

Wide local excision is the 'preferred initial intervention' by ACOG if invasive carcinoma is suspected, and, vulvar biopsy shows vulvar HSIL. If occult invasive disease is not suspected, vulvar HSIL treatment includes surgery: wide local excision, partial vulvectomy, skinning vulvectomy, or simple vulvectomy, laser ablation. Surgical treatments are associated with disruption of normal anatomy and subsequent issues with body image and sexual dysfunction. Medical therapies have been investigated as a means to avoid these negative outcomes. Clinical trials have shown the application of topical imiquimod to be effective however it has not been approved by the U.S. Food and Drug Administration for this indication. Inconsistent treatment efficacy results have been shown with photodynamic therapy, topical cidofovir and topical 5-flourouracil.

Vulvar HSIL may be followed (with interim observation, but, no intervention) if the patient is young, and, or, if the immune-compromised state is being corrected. Women with pathologic clear margins (no vulvar HSIL) after surgical excision have a lower, yet significant, risk of recurrence compared to women with involved margins. Laser ablation is acceptable treatment for vulvar HSIL when cancer is not suspected, although the risk of recurrence is slightly higher compared to wide local excision. Laser treatment of vulvar HSIL requires destruction of cells through the entire thickness of the epithelium including hair follicles (in hair-bearing areas of the vulva). In areas without hair, ablation should

extend through the dermis. Post-treatment recurrence rates exceed 30% (for all treatment regimens), and is higher with positive excision margins [14].

### 1.1.5 PSYCHOLOGICAL AND PHYSICAL IMPACTS OF CURRENT THERAPEUTIC OPTIONS

Virtually all patients with HPV-related Vulvar HSIL will require treatment, given the low rate of spontaneous resolution. According to the current ACOG & ASCCP guideline for management of VIN, because of the potential for occult invasion and if cancer is suspected (even if biopsy shows vulvar HSIL), the standard treatment of vulvar HSIL is wide local excision (i.e. surgery) [15]. When occult invasion is not a concern, vulvar HSIL can be treated with excision, laser ablation, or topical imiquimod as an off-label medical therapy.

Current treatment options are associated with pain, disfigurement and a recurrence rate as high as 45% at three years post-treatment [14]. Therefore, many patients have a fear of recurrence and progression to cancer [16].

In excisional treatment, patients are advised to rest for two weeks, including delaying return to work for up to one week, and to avoid sexual intercourse for up to 5 weeks. Furthermore, patients are instructed to avoid baths and exercise for a few weeks, and some women are advised to avoid use of toilet paper and to rather rinse with warm water. During recovery, common effects include pain in urinating and wiping, soreness, difficulty sitting, and feeling tired [17]. In the first week after hospital discharge, common patient-reported symptoms and other effects include swelling, drainage, pain, bleeding, numbness, redness, hardness, burning, pressure, unusual odor, changed skin color, opening of suture, warmth, itching, scarred skin, tiredness (including some feeling of exhaustion), insecurity, feeling of changed body, sexual concerns, anxiety, sadness, changed feeling in self-confidence, and difficulties in partnership [18].

### 1.1.6 IMPACT OF VULVAR HSIL UPON ACTIVITIES OF DAILY LIVING

The presence of vulvar HSIL is frightening and can have long-lasting effects on well-being [17]. The symptoms and signs of vulvar HSIL can be moderate to severe and include painful sexual intercourse, itching or burning, and visible lesions.

In the first week after hospital discharge from surgical excision, common patient-reported impacts on daily life include difficulties sitting, wearing clothes (e.g. underwear, pants), carrying out activities (e.g. climbing stairs, cooking), bowel movements, and urinating [18].

In a study of sexual function and quality of life after excisional treatment, vulvar HSIL patients reported significantly poorer scores in sexual function and quality of life than age-matched healthy women [19]. During the post-treatment follow-up phase of about one year, until given assurance of lesion clearance some patients report the sense that they are in the doctor's office all the time [17].

### 1.1.7 LIMITATIONS OF PROPHYLACTIC HPV VACCINES

Immunization with prophylactic vaccines represents the initial recommended approach within the pediatric and young female populations to avoid HPV-associated vulvar HSIL and subsequent vulvar cancer. The US-licensed prophylactic HPV vaccines are indicated for girls and women ages 9 through 26 years for Gardasil® and Gardasil®9 (Merck & Co. Inc.), and ages 9 through 25 years for Cervarix® (GlaxoSmithKline). The early portions of

these age ranges are generally before sexual debut and thus can allow immunologic protection against the anticipated earliest normal exposures to HPV infection. HPV prophylactic vaccination is highly effective and safe, and routine vaccination is recommended for females in the United States starting at age 11 or 12 years [20]. However, the prophylactic vaccines have no therapeutic effect upon existing HPV infection or existing HPV-related intraepithelial neoplasia [21]).

#### 1.1.8 ENHANCED MONITORING PLAN

An enhanced monitoring plan is used in this study to address the risk of a potential delay in treatment of vulvar HSIL. The feasibility of this approach was demonstrated in the Phase 2b study of cervical HSIL. Given that vulvar disease progresses slowly to vulvar cancer if untreated, the proposed enhanced monitoring plan is expected to maintain the safety of trial subjects for this study. First, only Gynecology-Oncologists and Gynecologists who are well experienced in the monitoring and management of vulvar disease will be used as study investigators. Inclusion into the study will require histologic confirmation of the diagnosis of the vulvar disease as vulvar HSIL, and not carcinoma, by two independent expert pathologists (pathology adjudication committee). Women with differentiated VIN, which is more likely to progress faster and is not typically HPV-related [22], is specifically excluded from study entry. By contrast, HPV-associated vulvar HSIL does not progress rapidly, typically taking years to manifest and progress, making enhanced monitoring feasible.

Throughout the study, there will be frequent vulvoscopy as well as photographic documentation and analysis of the lesion size (see Section 6.14). Colposcopy will also be done at baseline and during the study given that concurrent disease in the lower genital tract can occur. A Data Safety Monitoring Board will be utilized to review subject safety data and advise on any study-level safety concerns. Investigators always have the option of performing ad hoc vulvar biopsies to rule out disease progression. Additional treatment (e.g., additional excision, ablation, or medical therapy) may be carried out, if deemed necessary according to Investigator judgement.

#### 1.1.9 VGX-3100

VGX-3100 encodes HPV-16 E6/E7 and HPV-18 E6/E7 antigens. The plasmids were designed and constructed using proprietary synthetic vaccine (SynCon™) technology. This process involves synthetically deriving consensus genes across multiple strains and optimizing DNA inserts at the genetic level to allow high expression in human cells. Together, VGX-3100 and the CELLECTRA® device represent an integrated investigational product designed as a non-surgical treatment of HPV-16/18-related cervical HSIL (CIN2, CIN3) via an immune response directed against HPV-16/18. Further information about VGX-3100 is provided in the Investigator's Brochure.

#### 1.1.10 ELECTROPORATION

VGX-3100 is delivered using the CELLECTRA® *in vivo* electroporation (EP) device. EP is a physical method of tissue transfection whereby the generation of short, controlled electrical pulses creates a localized electric field at the injection site of the DNA vaccine which increases cell membrane permeability and improves the transfection of DNA and subsequent immunogenicity [23, 24]. Electroporation increases the uptake of plasmid DNA, thereby enabling increased expression and enhanced vaccine immunogenicity by

10 to 100 fold [25, 26]. This technology has been used for more than three decades by molecular biologists for cell transfection and has demonstrated versatility in use, as shown by its functionality in combination with a range of molecules, tissue types, disease indications, and across species [27].

This study will use the CELLECTRA® 2000 device which has been used in 26 trials with 3795 doses administered to human subjects as of September 30, 2016 with no significant safety issues identified. Further information about the CELLECTRA® 2000 device can be found in the Investigator's Brochure and device User Manual.

#### 1.1.11 IMIQUIMOD CREAM, 5%

Imiquimod Cream, 5% is a licensed product intended to be used in this study concomitantly with the investigational product and device. Imiquimod Cream, 5% will be centrally sourced, supplied in single-use packets (24 per box), each of which contains 250 mg of the cream, equivalent to 12.5 mg of imiquimod. The product manufacturer is Perrigo, Yeruham 80500, Israel.

#### 1.1.12 STUDY RATIONALE

This pilot study is being conducted in a population with vulvar dysplasia using a randomized, open-label design to demonstrate the efficacy of VGX-3100 followed by EP in women with vulvar HSIL associated with HPV-16/18 either alone or in combination imiquimod. The overall aim is to determine if treatment with VGX-3100 could allow women with vulvar HSIL to avoid or minimize surgical treatment procedures. Proof of concept that VGX-3100 can induce resolution of both HPV-associated dysplastic lesions and the underlying HPV 16/18 infection was shown in a Phase 2b study of cervical intraepithelial neoplasia (CIN). The similar underlying pathogenic mechanisms between cervical and vulvar HSIL form the basis of the clinical hypothesis that VGX-3100 could be a non-surgical therapeutic option for the treatment of vulvar HSIL, which is a significantly under met medical condition. A VGX-3100 with imiquimod-administration arm is also included, given the prevalent use of imiquimod as a topical medical treatment of vulvar lesions, to investigate if a more robust immune response is achieved with VGX-3100, to potentially increase regression of vulvar HSIL.

#### 1.1.13 DOSE AND REGIMEN RATIONALE FOR VGX-3100

A total dose of 6 mg VGX-3100 DNA has been selected for this study based on previous human experience with VGX-3100, preclinical data with VGX-3100 and other DNA vaccines, and the safety and immunogenicity data generated in the HPV-001, HPV-003, and HPV-101 studies. In HPV-001 trial, the 6 mg dose was delivered IM followed by EP, which showed trends toward higher response rates and magnitudes of IFN- $\gamma$  ELISpot responses compared to the low (0.6 mg) and mid-dose (2 mg) cohorts without significant safety issues [28].

#### 1.1.14 RATIONALE FOR IMIQUIMOD

Imiquimod cream is prescribed for the topical treatment of certain skin growths including external genital and perianal warts. Imiquimod may be able to be used synergistically with VGX-3100.

Randomized controlled trials have shown that the application of topical imiquimod 5% is effective for the treatment of vulvar HSIL although it is not approved by the US Food and Drug Administration for this purpose. Imiquimod is currently recommended as a non-surgical, off-label treatment option for vulvar dysplasia by the American College of Obstetricians and Gynecologists (ACOG). Published regimens include three times weekly application to affected areas for 12 – 20 weeks, with colposcopic assessment at 4-6 week intervals during treatment [15].

The current study will include an imiquimod arm with VGX-3100, to evaluate histopathologic regression of vulvar HSIL and virologic clearance of HPV-16/18, compared to the current body of knowledge in imiquimod alone.

#### 1.1.15 POTENTIAL RISKS OF INVESTIGATIONAL PRODUCTS

Based on the phase 1 and 2 clinical experience, the injection site reactions associated with the IM injection and electroporation are generally mild and limited to a few days in duration at most. The full risk profile for VGX-3100 is described in the Investigator Brochure.

Local skin and application site reactions are the most frequently reported adverse reactions associated with topical imiquimod 5% treatment. Erythema, erosion, excoriation/flaking, edema, induration, ulceration, scabbing, and vesicles have been reported at the application site [29]. The full risk profile of imiquimod 5% treatment is available in the package insert and prescribing information.

#### 1.1.16 POTENTIAL BENEFITS OF STUDY PARTICIPATION

This study has been designed to provide non-surgical treatment with the aim of avoiding the need for surgical excision or laser ablation, which can be disfiguring and have significant associated morbidity. In the absence of complete resolution of vulvar lesions, there would still be potential benefit from a partial response, which would minimize the amount of excisional therapy that may be needed. All currently accepted surgical treatments for VIN are associated with risks inherent with any surgical procedure including anesthesia, post-operative bleeding, infection, or damage to surrounding structures such as the clitoris, urethra, or anus. The other potential benefit is that the response to VGX-3100 is systemic and may clear the underlying HPV infection, which is the root cause of vulvar HSIL. Consequently, there is the potential to reduce the risk of recurrent disease.

## 2. HYPOTHESIS AND STUDY OBJECTIVES

Four 6 mg doses of VGX-3100 (DNA plasmids encoding E6 and E7 proteins of HPV-16 and HPV-18) delivered intramuscularly (IM) followed by electroporation (EP) with CELLECTRA® 2000 alone or in combination with imiquimod to adult women with histologically confirmed vulvar HSIL associated with HPV-16 and/or HPV-18 (HPV-16/18), will result in a higher percentage of women with regression of HSIL of the vulva based on histology (i.e. biopsies or excisional treatment) and virologic clearance of HPV-16/18 from vulvar tissue compared with historical control.

## 2.1 PRIMARY OBJECTIVE AND ENDPOINT

Objective	Endpoint
Determine the efficacy of four doses of VGX-3100, alone or in combination with imiquimod, with respect to combined histopathologic regression of vulvar HSIL and virologic clearance of HPV-16/18 in vulvar tissue	Proportion of subjects with no histologic evidence of vulvar HSIL and no evidence of HPV-16/18 at Week 48 in vulvar tissue samples (i.e. collected via biopsy or excisional treatment).

## 2.2 SECONDARY OBJECTIVES AND ASSOCIATED ENDPOINTS

Secondary Objectives	Associated Secondary Endpoints
1. Evaluate the safety and tolerability of VGX-3100 delivered IM followed by EP with CELLECTRA® 2000, alone or in combination with imiquimod	1a. Local and systemic events for 7 days following each dose as noted in the Participant Diary. 1b. All adverse events including SAEs, SUSARs, UADEs, and other unexpected AEs for the duration of the study (through Week 100 visit)
2. Determine the efficacy of four doses of VGX-3100, alone or in combination with imiquimod, as measured by histologic regression of vulvar HSIL	2. Proportion of subjects with no evidence of vulvar HSIL on histology (i.e. biopsies or excisional treatment) at Week 48 visit
3. Determine the efficacy of four doses of VGX-3100, alone or in combination with imiquimod, as measured by virologic clearance of HPV-16/18 in vulvar tissue	3. Proportion of subjects with no evidence of HPV-16/18 in vulvar tissue samples at Week 48 visit
4. Determine the efficacy of VGX-3100 , alone or in combination with imiquimod, as measured by histologic regression of vulvar HSIL to normal tissue	4. Proportion of subjects with no evidence of vulvar HSIL and no evidence of condyloma on histology (i.e. biopsies or excisional treatment) at the Week 48 visit
5. Determine the efficacy of four doses of VGX-3100 , alone or in combination with imiquimod, as measured by non-progression of vulvar HSIL to vulvar cancer as determined by histology	5. Proportion of subjects with no progression of vulvar HSIL to vulvar cancer from baseline to Week 48 visit

 No evidence of vulvar HSIL is defined as normal tissue or vulvar LSIL (VIN 1) or condyloma

 Clearance of HPV-16 or HPV-18 is defined as being undetectable by PCR assay.

 Progression is defined as advancement to carcinoma according to the Pathology Adjudication Committee by histology.


6. Determine the efficacy of VGX-3100, alone or in combination with imiquimod, as measured by reduction in the surface area of vulvar lesion(s)
	
6. Percent reduction in the cumulative surface area of the acetowhite vulvar lesion(s) as determined by the quantitative analysis of standardized photographic imaging at Week 48, 74 and 96 compared to baseline. Results will be classified as: no clinically significant lesion resolution (reduction in lesion size of 0-25%), partial lesion area resolution (>25% and <100% reduction), and complete lesion resolution (no visible lesion).

7. Describe the humoral and cellular immune response of VGX-3100 administered alone or in combination with imiquimod, post dose 3, post dose 4, and after additional dosing
	
7a. Levels of serum anti-HPV-16 and anti-HPV-18 antibody concentrations at baseline, Weeks 15, 27, 48, 74, and 96 visits 7b. Interferon-<math>\gamma</math> ELISpot response magnitudes at baseline and Weeks 15, 27, 48, 74 and 96 visits 7c. Flow Cytometry response magnitudes at baseline and Week 27 visits

 Digital photos will be analyzed with a computer program to calculate the total lesion size in cm^2.

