## 8. STATISTICAL ANALYSIS PLAN

### 8.1 GENERAL CONSIDERATIONS

The statistical analysis of the data will be performed by Inovio Pharmaceuticals or its representative.

This is a two-arm, multi-center, open-label randomized clinical trial of VGX-3100 and VGX-3100 with imiquimod, in subjects with a histologic diagnosis vulvar HSIL and confirmed vulvar infection with HPV types 16 and/or 18. The study's primary endpoint is binary: regression of vulvar HSIL and viral clearance of HPV-16 and/or HPV-18 from vulvar tissue based on tissue collected at Week 48. The primary hypothesis is that each of the treatment arms will result in regression of HSIL and clearance. Secondary efficacy analyses pertain to regression, clearance of HPV-16 and/or HPV-18 infection, regression to normal, non-progression, and anatomic extent. Other secondary analyses concern safety and humoral and cellular immunological measures. Exploratory efficacy analyses concern extended dosing with respect to regression, clearance, and anatomic extent, clearance outside of the vulva, and effect of HLA type on efficacy. Other exploratory analyses pertain to tissue immunological measures, effect of needle depth into muscle on efficacy, and patient-reported outcomes.

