## 8.9 EFFICACY ANALYSIS

The true treatment effect on the primary endpoint is  $p$ , where  $p$  denotes the true population probability of the primary endpoint for each arm. The primary hypothesis of superiority is:  $H_0: p \leq 0.02$  vs.  $H_1: p > 0.02$ , for each treatment arm separately.

A p-value for these hypothesis tests and corresponding 95% confidence intervals will be computed based on the method of Clopper-Pearson. Superiority will be concluded if the one-sided p-value is  $< 0.025$  and the corresponding lower bound of the 95% CI exceeds 0.02.

The secondary efficacy binary endpoints will be analyzed in the same manner as the primary hypothesis, but without the hypothesis test p-values.

For the analyses, the efficacy time frame is defined by any time starting from 14 days prior to the -specified visit week.

The anatomic extent endpoint will be analyzed by calculating the mean percent change and associated 95% t-distribution based confidence interval. The percentage of subjects with no clinically significant lesion resolution (reduction in lesion size of 25% or less), partial lesion resolution (26-99% reduction), and complete reduction (100% reduction) will be summarized with point estimates and associated Clopper-Pearson 95% confidence intervals.

An exploratory analysis will examine clearance outside of the vulva. This will be analyzed in the same manner as vulvar clearance.

An exploratory analysis will examine the relationship between the primary efficacy endpoint and HLA results. As these results are categorical, relationships will be examined with contingency tables and logistic regression models which model the primary endpoint versus these results and treatment group as regressor variables.

An exploratory analysis will examine the relationship between the primary efficacy endpoint and needle depth into muscle. A logistic regression model which models the primary endpoint versus these results and treatment group as regressor variables will be used.

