4. Determine the efficacy of four doses of VGX-3100 , alone or in combination with imiquimod, as measured by histologic regression of vulvar HSIL to normal tissue	4. Proportion of subjects with no evidence of vulvar HSIL and no evidence of condyloma on histology (i.e. biopsies or excisional treatment) at the Week 48 visit
5. Determine the efficacy of four doses of VGX-3100 , alone or in combination with imiquimod, as measured by non-progression of vulvar HSIL to vulvar cancer as determined by histology	5. Proportion of subjects with no progression  of vulvar HSIL to vulvar cancer from baseline to Week 48 visit
6. Determine the efficacy of VGX-3100, alone or in combination with imiquimod, as measured by reduction in the surface area of vulvar lesion(s)	6. Percent reduction in the cumulative surface area of the acetowhite vulvar lesion(s) as determined by the quantitative analysis of standardized photographic imaging at Week 48, 74 and 96 compared to baseline  . Results will be classified as: no clinically significant lesion resolution (reduction in lesion area of 0-25%), partial lesion area resolution (>25% and <100% reduction) and complete lesion resolution (no visible lesion).

 No evidence of vulvar HSIL is defined as normal tissue or vulvar LSIL (VIN 1) or condyloma

 Clearance of HPV-16 or HPV-18 is defined as being undetectable by PCR assay.

 Progression is defined as advancement to carcinoma by histology according to the Pathology Adjudication Committee.

 Digital photos will be analyzed with a computer program to calculate the total lesion size in cm^2.

7. Describe the humoral and cellular immune response to VGX-3100, administered alone or in combination with imiquimod, post dose 3, post dose 4, and after additional dosing
	
7a. Levels of serum anti-HPV-16 and anti-HPV-18 antibody concentrations at baseline, Weeks 15, 27, 48, 74 and 96 visits 7b. Interferon-<math>\gamma</math> ELISpot response magnitudes at baseline and Weeks 15, 27, 48, 74 and 96 visits 7c. Flow Cytometry response magnitudes at baseline and Week 27 visits

Exploratory Objectives
	
Associated Exploratory Endpoints

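### Secondary endpoint 4 is meant to measure regression to normal tissue but, as written, also counts Week 48 biopsies showing LSIL (VIN 1)

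*Protocol*

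**What the plan says.** The objective, in the synopsis and again in the Section 2.2 table, is "histologic regression of vulvar HSIL to normal tissue". The endpoint in the same row is the proportion of subjects with "no evidence of vulvar HSIL and no evidence of condyloma" on Week 48 histology.

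The footnotes to the same tables (footnote 5 in the synopsis, footnote 11 in Section 2.2) state: "No evidence of vulvar HSIL is defined as normal tissue or vulvar LSIL (VIN 1) or condyloma". Section 1.1.3 explains the low-grade term: "the term 'vulvar LSIL' will be used to encompass what was previously known as VIN 1".

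Section 8.1 lists the analysis under the name regression to normal: "regression to normal, non-progression, and anatomic extent". Section 8.9 says of this class of endpoint: "The secondary efficacy binary endpoints will be analyzed in the same manner as the primary hypothesis, but without the hypothesis test p-values". It would therefore be a proportion with a Clopper-Pearson 95% interval and no test.

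The protocol file holds three successive versions. The synopsis and Section 2.2 wording is the same in all three, including the latest, Version 1.2. The available text of Version 1.2 stops in Section 6, so Sections 8 and 10 can be read only in Versions 1.0 and 1.1. The point rests on the synopsis and Section 2.2 of Version 1.2.

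**The concern.** Endpoint 4 stands beside endpoint 2, which is the proportion with no HSIL. It adds something only if it separates women whose tissue has become normal from women who have merely lost the high-grade component. LSIL is the obvious finding between those two states, and the protocol names it as a non-HSIL finding distinct from normal tissue. Endpoint 4 does not exclude it. As written, endpoints 2 and 4 can differ only by women with condyloma.

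At stake is what a secondary result means. A rate reported under a heading of regression to normal will be read as the proportion with normal histology, yet it may include women with residual VIN 1. The SAP cannot settle this quietly. If it follows the endpoint, LSIL is reported under a normal-tissue heading. If it follows the objective, it departs from the protocol's stated endpoint.

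**Working it through.** The protocol states no expected figure for endpoint 4, so there is nothing to reproduce. The check is one of set membership, followed by the size of one case.

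**Step 1: what each rule accepts.** Inputs are the endpoint 2 and endpoint 4 wording and the footnote definition, all in Section 2.2 and the synopsis.

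| Week 48 PAC finding | Endpoint 2 (no HSIL) | Endpoint 4 as written | Objective 4 (normal tissue) |
|---|---|---|---|
| Normal tissue | success | success | success |
| LSIL (VIN 1) | success | **success** | **failure** |
| Condyloma | success | failure | failure |
| HSIL | failure | failure | failure |
| Carcinoma | failure | failure | failure |

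As sets:
- Endpoint 2 accepts {normal, LSIL, condyloma}.
- Endpoint 4 accepts {normal, LSIL, condyloma} minus {condyloma} = {normal, LSIL}.
- Objective 4 calls for {normal}.

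Endpoint 4 and its objective disagree on LSIL only. Endpoint 4 and endpoint 2 disagree on condyloma only.

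**Step 2: does this depend on the footnote marker?** The marker is attached to endpoint 2, not endpoint 4. The result is the same without it, because a biopsy read as VIN 1 is neither HSIL nor condyloma and so passes endpoint 4 on its plain words.

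**Step 3: size per case.** Section 8.3 gives 36 subjects randomised 2:1 with 90% evaluable at Week 48; Section 3 gives arms of 24 and 12.
- VGX-3100 alone: 24 × 0.9 = 21.6, about 22. One case = 1/22 = 4.5 percentage points.
- Combination: 12 × 0.9 = 10.8, about 11. One case = 1/11 = 9.1 percentage points.

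If L women in an arm of n evaluable subjects have LSIL with neither HSIL nor condyloma, the overstatement is L/n. The protocol gives no value for L.

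**Step 4: illustration only; the counts are assumed.** Clopper-Pearson 95% intervals:
- VGX-3100 alone, 4 of 22 meeting endpoint 4 as written: 18.2% (5.2 to 40.3). With one of the four LSIL, regression to normal is 3/22 = 13.6% (2.9 to 34.9). With two, it is 2/22 = 9.1% (1.1 to 29.2). With none, it stays at 18.2%.
- Combination, 3 of 11: 27.3% (6.0 to 61.0). With one of the three LSIL, it is 2/11 = 18.2% (2.3 to 51.8).

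**The case against.** **The endpoint is explicit.** It can be computed without ambiguity, and a report quoting its text would say nothing false. The pathology reading would also be correct, so no biopsy is misread. This stands, and it defines the fault: the objective and the endpoint attached to it do not match. It does not remove the fault, because the objective and Section 8.1 both give the result a name that the endpoint does not earn.

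**LSIL and condyloma may overlap in the PAC's coding.** The protocol does not say that they are mutually exclusive, and the PAC's reading categories are not shown. A woman with both findings would already fail endpoint 4. This stands as a limit on the count: only LSIL without condyloma is wrongly included. The footnote lists the two as alternatives, so some LSIL-only results must be expected as possible.

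**The endpoint is secondary.** It is reported as an estimate with an interval and no p-value, and endpoint 2 separately reports loss of HSIL. This stands and limits the consequence.

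**Readings that go too far.** A reader might assume an LSIL frequency of, say, 5 to 15% and call the bias large against the 20% response rate in Section 8.3. The documents do not support that. They give no LSIL frequency, and the 20% is the assumed rate for a different endpoint (regression together with HPV-16/18 clearance) in the VGX-3100-alone arm; the combination arm assumes 28%. A reader might also infer that the primary endpoint is faulty because it too accepts LSIL. It is not: its objective is regression of HSIL with viral clearance, and the protocol openly defines absence of HSIL to include LSIL and condyloma.

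**Conclusion.** Wrong as written, and it should be corrected. In the current synopsis and Section 2.2, endpoint 4 does not measure objective 4: it counts normal tissue plus LSIL (VIN 1). It overstates regression to normal by the number of women whose Week 48 histology shows LSIL but neither HSIL nor condyloma. That number is unknown and may be zero. With arms this small, each case matters to the estimate: about 4.5 points at 22 evaluable and about 9 at 11, assuming the planned 90% evaluability.

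The conclusion assumes that the PAC records LSIL separately from normal tissue and condyloma, as the protocol's own list implies. It does not extend to the primary endpoint, the responder definition, the sample size or the power, none of which uses endpoint 4.

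**What to change.** In both the synopsis and Section 2.2, reword endpoint 4 as the proportion of subjects with *no HSIL, no LSIL (VIN 1) and no condyloma at Week 48, by PAC diagnosis*. Use PAC diagnosis rather than PAC consensus: Section 10.4.2 (readable in Versions 1.0 and 1.1) describes agreement between two readers, then any two of three, with joint review only as a last step. Requiring consensus would add a new standard.

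If the sponsor did intend LSIL to count, leave the endpoint alone and rename objective 4, and its label in Section 8.1, so that neither refers to normal tissue. Either change removes the mismatch. It should be settled before Week 48 histology is summarised, and the SAP should carry the same wording.

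The cost is one phrase in two places. PAC diagnoses are already obtained for every biopsy, so no new data should be needed provided LSIL is recorded as its own category. With LSIL excluded, the reported rate can only stay the same or fall, so the correction cannot favour the product.
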